### **Data analysis:**

- Vital values: Gaps in vital value data were not imputed.  
Durations will be calculated in minutes per 24 hours (1440 minutes) of monitoring.
- Data will be presented with descriptive statistics.  
Categorical data will be tested with Fishers exact test.  
Continuous data will be tested with Wilcoxon Mann-Whitney U test.  
Time-till-event will be tested with cox-regression.
- For statistical tests and alpha of < 0.05 will be considered statistically significant.

**Table 1: Patient demographics**

	Control arm N = 200	Intervention arm N = 200
Age, mean		
Male, no (%)		
ASA class		
I		
II		
III		
>IV		
Smoking status		
Never smoked		
Former smoker		
Current smoker		
Pack years for former and current smokers (mean)		
Preexisting conditions, n (%)		
COPD		
Vascular insufficiency		
Chronic arterial hypertension		
Diabetes Mellitus		
Type of surgery		
Abdominal		
Vascular		
Urologic		
Orthopedic		

**Table 2: Primary outcomes - Cumulative duration of deviating vital values per 24 hours**

	Intention to treat analysis		
	Control arm N = 200	Intervention arm N = 200	p-value
Total cumulative			
Respiratory			
SpO 2 < 92 %			
SpO 2 < 88 %			
SpO 2 < 85 %			
SpO 2 < 80 %			
RF < 5 min 			
RF < 11 min 			
RF > 24 min 			
RF > 30 min 			
Circulatory			
HR < 30 min 			
HR [30 - 40] min 			
HR > 110 min 			
HR > 130 min 			
SBP < 70 mmHg			
SBP < 90 mmHg			
SBP > 180 mmHg			
SBP > 220 mmHg			

**Table 3: Secondary outcomes - Median number of alarms for sustained deviations per 24 hours. For control patients the number is the theoretical number of alarms a system would issue.**

	Control arm N = 200	Intervention arm N = 200	p-value
Desaturation			
SpO2 < 92 % for > 60 min			
SpO2 < 88 % for > 10min			
SpO2 < 85 % for > 5 min			
SpO2 < 80 % for > 1 min			
Bradypnea			
RF < 5 min  for > 1 min			
RF < 11 min  for > 15 min			
Tachypnea			
RF > 24 min  for > 15 min			
RF > 30 min  for > 5 min			
Bradycardia			
HR < 30 min  for > 1 min			
HR [30 - 40] min  for > 5 min			
Tachycardia			
HR > 110 min  for > 60 min			
HR > 130 min  for > 30 min			
Hypotension			
SBP < 70 mmHg for > 30 min			
SBP < 90 mmHg for > 60 min			
Hypertension			
SBP > 180 mmHg for > 60 min			
SBP > 220 mmHg for > 30 min			

**Table 4: Tertiary outcomes**

	Intention to treat analysis		Per protocol analysis	
	Control arm N = 200	Intervention arm N = 200	Control arm N = 280	Intervention arm N = 120
Serious Adverse Events at 7 days / n (%)	XX (xx %)	XX (xx %)	XX (xx %)	XX (xx %)
Serious Adverse Events at 30 days / n (%)	XX (xx %)	XX (xx %)	XX (xx %)	XX (xx %)
Death / n (%)	XX (xx %)	XX (xx %)	XX (xx %)	XX (xx %)
Length of stay / days [IQR]	X [X-XX]	X [X-XX]	X [X-XX]	X [X-XX]
Reoperation / n (%)	XX (xx %)	XX (xx %)	XX (xx %)	XX (xx %)

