**Secondary Outcome Measures:**

- *Frequency of sustained deviation alerts*

*Frequency of each of the sustained deviations in vital signs. List of vital signs, and normal limits detailed in protocol.*

Number of alarms are calculated as the number of alarms per 24 hours.

*[Time Frame: First 5 days from randomization or until discharge, whichever comes first]*

- *AE during the first 7 days and the first 30 days*
- *SAE during the first 7 days and the first 30 days*

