### **Outcome analysis:**

- *Intention to treat analysis*
  - Patient outcomes are analyzed based on the randomization groups.
- *Per-protocol analysis*
  - Patients included in the intervention are those with:
    - intervention patients with alerts with at least one registered use of the app in relation to an alert, as indicated if the “attend”, “postpone/snooze” or “transfer” buttons have been used.
  - OR
  - intervention patients with no alerts, are also included in the intervention group.

AND

- at least 12 hours of monitoring with valid data transfer.
- Patients in the control-group are all patients from the control group with at least 12 hours of monitoring.

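### Table 4 prints a per-protocol control group of 280, but the SAP's own rule caps it at the 200 patients randomised to control

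*SAP*

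**What the plan says.** The Outcome analysis section of the SAP defines two analysis sets.

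- **Intention to treat:** "Patient outcomes are analyzed based on the randomization groups".
- **Per protocol, intervention:** the set takes "intervention patients with alerts with at least one registered use of the app in relation to an alert", together with intervention patients who had no alerts. It also requires "at least 12 hours of monitoring with valid data transfer".
- **Per protocol, control:** "Patients in the control-group are all patients from the control group with at least 12 hours of monitoring".

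Table 1 gives "Control arm N = 200". Tables 2 and 3 and the intention-to-treat columns of Table 4 use the same figure, with 200 in the intervention arm as well. The per-protocol columns of Table 4 are headed "Control arm N = 280" and "Intervention arm N = 120". The result cells of Table 4 are unfilled.

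**The concern.** The header and the rule describe different analysis sets. Under the rule, a per-protocol set can only lose patients relative to the randomised arm. The header shows the control group gaining 80.

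The Outcome analysis section lists who enters each group. By those lists, an intervention patient who fails the criteria belongs to neither group, but the section does not say so in words. A reader who sets that silence beside 280 and 120 could conclude that such patients are to be counted as controls. That would be an as-treated comparison carrying a per-protocol label.

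The rows affected are SAEs at 7 and 30 days, death, length of stay and reoperation. The SAEs are listed among the secondary outcomes ("SAE during the first 7 days and the first 30 days"). Under the written rule, an intervention patient fails either by having alerts with no registered app use or by having too little valid monitoring. Both are known only after randomisation. Moving such patients into the control column would give up the protection of randomisation and open the comparison to selection bias.

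**Working it through.** **Inputs, all from the SAP**

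- Randomised to control: 200 (Tables 1 to 3; Table 4, intention to treat)
- Randomised to intervention: 200 (same places)
- Per-protocol header, control: 280 (Table 4)
- Per-protocol header, intervention: 120 (Table 4)
- Per-protocol control rule: a subset of the control arm (Outcome analysis)
- Per-protocol intervention rule: a subset of the intervention arm (Outcome analysis)

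**1. Can the rule give the printed control N?** Per-protocol controls are a subset of the control arm, so N ≤ 200. The header exceeds this by 280 − 200 = 80. The rule cannot reproduce 280.

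**2. Can the rule give the printed intervention N?** 120 ≤ 200, so yes. Taken alone, 120 is compatible with the rule.

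**3. The pair.** With 120 intervention patients, the rule allows at most 120 + 200 = 320 patients. The header totals 280 + 120 = 400, and 400 − 320 = 80. This is the excess from step 1 seen in the total, not a second error. Under the rule a total of 400 can arise only as 200 and 200.

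**4. What would produce 280?** Suppose every intervention patient outside the per-protocol intervention group were counted as a control: 200 + (200 − 120) = 280. This matches exactly. The total is unchanged (200 + 200 = 400 and 280 + 120 = 400), so the number excluded would be 400 − 400 = 0, including nobody for short monitoring. The SAP contains no rule of this kind, so this is a reading that fits the figures and not a documented intention.

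**5. Size of the mixing if the header were followed.**

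- Share of the control column randomised to intervention: 80 / 280 = 28.6%
- Share of the intervention arm reassigned: 80 / 200 = 40%

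The SAP gives no event rates for these patients, so neither the size nor the direction of a resulting bias can be computed.

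**The case against.** The strongest reply is that Table 4 is an empty shell. The Ns are round, the result cells hold only X's, and a header N is the output of a population rule, not an instruction. The header does not say which patients would move, so nobody could follow it; an analyst applying the written rule would simply overwrite it. On this view the 28.6% and 40% describe a hypothetical analysis, and the point is minor. The reach is also limited: per-protocol columns appear only in Table 4, which has no p-value column, and the primary-outcome table is headed intention to treat only. The protocol, which is not at hand, may define the population further.

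Much of this stands. The as-treated reading is unproven, the equal shifts and the unchanged total are one fact, and the primary intention-to-treat comparison does not depend on 280. The contradiction remains, however. A placeholder should at least be possible under the rule it illustrates; 120 is and 280 is not. The same header row prints 200 and 280 for the control arm. A reading error in the PDF is unlikely, since the two per-protocol figures add to exactly 400. Nothing in the SAP produces 280, and the SAP does not say in words what happens to an intervention patient who fails the criteria.

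**Conclusion.** The point holds. A per-protocol control N of 280 is impossible under the SAP's only written rule for that set, exceeding the maximum by 80. This rests on one assumption: that the 200 shown for the control arm throughout is the number randomised to control, which follows from the SAP's definition of intention to treat. If the randomised number turns out differently, the cap becomes that number, and a per-protocol control group larger than its own arm remains impossible.

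The document does not show whether the header or the rule reflects the sponsor's intent. The mixing of 28.6% of controls arises only if the header is followed. The discrepancy should be fixed before analysis, because it decides who enters the per-protocol comparison of SAEs, death, length of stay and reoperation.

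**What to change.** Replace both per-protocol headers in Table 4 with N = XX, to be filled in after the rule is applied and never larger than the number randomised to that arm (200 as planned). Add one sentence to the per-protocol definition, for example: *Patients who do not meet the criteria of their randomised arm are excluded from the per-protocol analysis and are not moved to the other arm.* If the sponsor does want an as-treated comparison, define the reallocation rule, present it separately from the per-protocol columns and label it exploratory.

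The cost is two column headers and one sentence. The per-protocol set will be smaller than 400 if any patient fails a criterion. The change does not remove the selection that comes from applying the app-use condition to one arm only, so the per-protocol results will still need cautious reading.
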